11.4. Analysis populations

All participants registered will be included in the analysis.

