9.13. Early Discontinuation/Withdrawal of Participants

During the course of the study a participant may choose to withdraw early from the study at any time. This may happen for several reasons, including but not limited to:

- The occurrence of what the participant perceives as an intolerable AE.
- Inability to comply with study procedures
- Participant decision

Participants may choose to stop study assessments but may remain on study follow-up.

Participants may also withdraw their consent, meaning that they wish to withdraw from the study completely. In the case of withdrawal before completing the 30 months of study participation and without completing the 6 research visits, the following options for a tiered withdrawal from the study will be available to participants:

 Participants may withdraw from further research visits, and further communication but allow the study team to continue to access their medical records and any relevant hospital data that is recorded as part of routine standard of care; e.g., scans, blood results and disease progression data etc.

- 2) Participants can withdraw from the study but permit data obtained up until the point of withdrawal to be retained for use in the study analysis. No further data would be collected after withdrawal.
- 3) Participants can withdraw completely from the study and withdraw the data collected up until the point of withdrawal. The data already collected would not be used in the final study analysis.

In addition, the Investigator may discontinue a participant from the study MRI procedures at any time if the Investigator considers it necessary for any reason including, but not limited to:

- Pregnancy
- Ineligibility (either arising during the study or retrospectively having been overlooked at screening)
- Significant protocol deviation
- Significant non-compliance with the study requirements Clinical decision (e.g. patient no longer suitable for ongoing surveillance)

Participants who withdraw will not be replaced as the sample calculation already allows for attrition.

The type of withdrawal and reason for withdrawal will be recorded in the CRF.

If the participant is withdrawn due to disease progression or an adverse event, the Investigator will arrange for follow-up visits or telephone calls until the adverse event has resolved or the participants condition optimised.

Procedures to minimise attrition

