11.2. Description of the Statistical Methods

Statistical analysis for Primary outcome measure

Measures of diagnostic performance will be determined per round of surveillance and over the 30 months of study participation.

Diagnostic performance per round of surveillance

At each round of surveillance, the following data will be calculated and compared between USS and nceMRI.

- 1. Number and proportions of positive surveillance USS and nceMRI see section 9 for definitions of positive tests
- Number and proportions of true positive (TP) and false positive (FP) USS and nceMRI. As each positive test will be followed by a full contrast enhanced MRI, TP and FP tests per round of surveillance will be calculated
- 3. Positive predictive value (PPV) of USS and nceMRI

Diagnostic performance for the overall study period of 30 months

For the purpose of this analysis, each USS and nceMRI scan for each participant completing the study will be assigned only one of the 4 possible diagnostic categories of: true positive (TP) or false positive (FP), true negative (TN) and false negative (FN). The sum of TP, FP, TN and FN in this analysis will therefore be equal to the total number of participants completing the study. TP and FP will be determined at each visit as described above. TN and FN will be determined at the end of the study when participants undergo the reference standard ceMRI as part of the study protocol. FN results will also include those cases that present with HCC during the study without a prior positive test (interval cancers) or cases where both USS and nceMRI are negative tests but a ceMRI scan is triggered by an AFP>20. Cases that are initially FP may subsequently change diagnostic category. For this analysis, the diagnostic category which is applicable at the end of the study will be used. For example, if a finding initially classed as an FP develops into an HCC that was correctly identified by the surveillance tests, then the diagnostic test will be counted as a TP for this analysis.

Sensitivity and specificity estimates will be calculated separately for nceMRI and USS and compared. Statistical significance of the observed differences in sensitivity/specificity will be evaluated using the McNemar's test of paired proportions, with a two-tailed P-value <0.05 used as the significance criteria.

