Extrahepatic: Extrahepatic incidental findings will be documented on the study proforma and assessed for likely significance. If a significant incidental finding is noted outside the liver this will be documented. Subsequent follow-up investigations will be recorded, as well as any significant diagnoses. Incidental findings in organs outside the liver will be managed according to local clinical routine, and not be counted as TP or FP when calculating sensitivity and specificity of nceMRI/USS.

Statistical analyses for secondary outcome measures

- 1. At each surveillance round, graphical methods will be used to analyse data for the numbers of:
 - a. very early, early, intermediate and advanced stage HCC as defined by the Barcelona Clinic Liver Cancer Staging system
 - b. the size and number of HCC, in TP cases
 - c. The number of new indeterminate lesions
- 2. Graphical methods will be used to analyse data on the number and proportions of participants with HCC who receive treatment with curative intent.
- 3. Quality of life and anxiety and depression: QoL will be assessed using the EQ-5D-5L questionnaire and anxiety and depression using the Hospital Anxiety and Depression Scale (HADS). Patients will be asked to complete the questionnaires at 6 monthly intervals to coincide with their visits for MRI / USS. Associations of the results from these questionnaires with other variables will be explored, particularly with HCC diagnosis and FP surveillance tests.
- 4. Acceptability of MRI and USS as surveillance tests: Patients will be asked to complete questionnaires documenting their experience of USS and MRI at the baseline visit and visit 5. These questionnaires have already been developed based on the questionnaires used in the METRIC study⁴¹, which assessed the acceptability of USS and MRI in patients with Crohn's disease. Scores derived from these questionnaires will constitute the outcome measure and they will be compared between nceMRI and USS.
- 5. Feasibility of nceMRI and USS as surveillance tools: To measure feasibility of nceMRI and USS as a surveillance tool, data will be collected on the number and reasons for missed scans. In particular we will determine if scans were cancelled by the hospital due to capacity issues, if the patient was lost to follow-up, or surveillance for HCC is no longer indicated. This data will be analysed using graphical methods.

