11.7. The Level of Statistical Significance

Statistical significance will be set at p<0.05.

11.8. Procedure for Accounting for Missing, Unused, and Spurious Data.

Participants must attend the baseline and last visit (v6) and have at least one ceMRI (after a positive surveillance test, or as per protocol at the end of the study period) in order to be included in the final analysis. Participants who do not meet this will be removed and replaced for the purposes of the statistical analysis. All data from participants that fulfil this criterion will be used and analysed using intention to diagnose methods. This is to ensure that cases where a participant completes one surveillance test but not the other at a particular visit are still included. The diagnostic category of the missed test will be determined according to the diagnosis on that visit and the final diagnosis at the end of the study. In cases of HCC diagnosis, the missed test will be assigned as FN. In cases of FP results on the surveillance test performed at that visit, the missed test will also be assigned as FP.

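### Sections 11.4 and 11.8 set conflicting analysis populations; read literally, 11.8 drops earlier-round results of HCC-free participants who never reach visit 6

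*Protocol*

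**What the plan says.** Three places in the protocol define who is analysed.

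- Section 11.4, under the heading for analysis populations, consists of one sentence: "All participants registered will be included in the analysis".
- Section 11.8, on missing data, states: "Participants must attend the baseline and last visit (v6) and have at least one ceMRI" to enter the final analysis. It continues: "Participants who do not meet this will be removed and replaced for the purposes of the statistical analysis". No outcome is named.
- Section 11.2, for the 30-month analysis only, states: "The sum of TP, FP, TN and FN in this analysis will therefore be equal to the total number of participants completing the study".

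For the per-round analysis, section 11.2 sets no completer condition: "As each positive test will be followed by a full contrast enhanced MRI, TP and FP tests per round of surveillance will be calculated". Per-round TP, FP and PPV are listed under the primary objective in section 6.

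The feasibility outcome in section 6 includes the number of participants lost to follow-up and the number for whom surveillance has ceased to be indicated. Section 11.2 (secondary outcomes, item 5) collects whether scans were missed because of hospital capacity, "if the patient was lost to follow-up, or surveillance for HCC is no longer indicated".

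Section 9.13 offers tiered withdrawal. Under option 2, data gathered before withdrawal stay available for analysis; only option 3 removes them.

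**The concern.** A registered participant who never attends visit 6 is inside the analysis under 11.4 and outside it under 11.8, and nothing says which section yields for which outcome. That matters most for outcomes that do not depend on visit 6. Someone who remains free of HCC but withdraws, is transplanted, dies or progresses to Child-Pugh C at about month 18 has already been scanned in several rounds. Any positive test in those rounds was to be followed by its own ceMRI.

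If 11.8 governs, those rounds disappear. The per-round results then describe people who stayed well enough to reach month 30. Section 9.13 itself expects losses from progression to Child-Pugh C and from comorbidity, so removal is likely to be related to disease severity. With the choice left open, the per-round denominators could also be settled after results are known.

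**Working it through.** **Step 1. What each outcome needs, against the two rules.**

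| Outcome | Needs, per protocol | Visit 6 needed? | Under 11.4 | Under 11.8 as worded |
|---|---|---|---|---|
| Per-round positives, FP, PPV (11.2) | That round's tests and the ceMRI after a positive | No | All registered | Leavers removed |
| 30-month TN and FN, hence sensitivity and specificity (11.2) | Mainly the end-of-study ceMRI | Yes, for TN and most FN | All registered | Visit 6 attenders with a ceMRI |
| Lost to follow-up, surveillance not indicated (6; 11.2 item 5) | A record of leaving | No; leaving is the event | All registered | Leavers removed |
| Data kept under withdrawal option 2 (9.13) | Consent to retain | No | Used | Discarded |

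The rows where 11.4 and 11.8 differ although visit 6 is not needed are the ones at issue. In the 30-month row the two sections also differ, and 11.2 sides with 11.8.

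**Step 2. Which per-round quantities move.** At a given round let T participants be tested, with TP and FP for one modality. Remove HCC-free leavers: t of the tested, carrying f false positives.

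- TP is unchanged, because these participants have no HCC.
- FP becomes FP − f.
- PPV changes from TP/(TP + FP) to TP/(TP + FP − f). With TP fixed, it can only stay the same or rise.
- The proportion positive changes from (TP + FP)/T to (TP + FP − f)/(T − t), which can move either way.

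**Step 3. How much data.** The protocol gives no attrition rate; section 9.13 says only that the sample size allows for attrition, and section 11.3 shows no figure. So there is no planned figure to reproduce. Inputs:

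- 300 participants and six rounds (protocol).
- A fraction a leaving before visit 6, taken as 10%, 20% or 30% (assumed).
- An average of three rounds done before leaving (assumed).
- Stayers complete all six rounds (simplification).

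Rounds discarded = 300 × a × 3. Rounds kept = 300 × (1 − a) × 6. Share discarded = discarded / (discarded + kept).

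| a | Participants removed | Discarded | Kept | Share discarded |
|---|---|---|---|---|
| 0.10 | 30 | 90 | 1620 | 90/1710 = 5.3% |
| 0.20 | 60 | 180 | 1440 | 180/1620 = 11.1% |
| 0.30 | 90 | 270 | 1260 | 270/1530 = 17.6% |

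As a check, replace the three-round average by a constant loss per round that reaches the same totals by visit 6. This gives 89 of 1709 rounds (5.2%), 175 of 1615 (10.8%) and 257 of 1517 (17.0%), so the result does not hinge on the three-round assumption.

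**Step 4. The other reading.** If the final analysis in 11.8 means only the 30-month analysis, the discarded rounds in Step 3 become zero and the feasibility counts are intact. Section 11.4 would still put all registered participants into an analysis from which 11.8 removes some of them.

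**The case against.** The strongest reply is that 11.8 was never meant to reach the per-round outcomes. Section 11.2 treats the two analyses under separate headings and attaches the completer denominator only to the second. Section 11.8 speaks of a final analysis, and it assigns missed tests partly from the diagnosis at the end of the study, which suits the 30-month table. Its rule could simply be the working definition of the completers in 11.2. This is a fair reading and cannot be excluded. But the next sentence of 11.8 removes people for the statistical analysis without limit, and its missed-test rule works visit by visit. The per-round consequence is therefore conditional, while the contradiction with 11.4 is not.

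It can also be said that populations by outcome belong in the SAP, which is not shown. That would answer an omission; it does not answer two protocol sentences that disagree.

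A reader might infer more than the documents support:

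- **That per-round true positives are lost.** HCC-free leavers contribute none. Participants whose HCC is diagnosed before visit 6 raise a separate question about the same sentence, not argued here.
- **That losses would be reported as about zero.** This is the literal extreme. It would contradict the outcome's own definition in section 6, and section 9.13 requires the type of and reason for withdrawal to be recorded. Missed appointments among those who reach visit 6 would be counted on any reading.
- **That every earlier result of a leaver is settled.** Under section 9.8.1 the on-study ceMRI settles LI-RADS 1, 2 and 5; LI-RADS 3 and 4 stay indeterminate. Section 7 has the per-round analysis record these as indeterminate.
- **That PPV or the nceMRI–USS comparison is shown to be biased.** Most discarded rounds would be negative scans, which do not enter PPV, and no false-positive counts are available from which to size the change.

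**Conclusion.** The point holds as a stated contradiction. Sections 11.4 and 11.8 cannot both apply, and no sentence assigns either to an outcome. On the literal reading of 11.8, HCC-free participants who leave early drop out of per-round FP, PPV and the denominators of per-round proportions, against withdrawal option 2 and against the purpose of the feasibility outcome. On the narrower reading, those data survive and only the conflict over the 30-month analysis remains.

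The size on the literal reading is about 5–18% of completed rounds. It rests on an assumed 10–30% loss and about three rounds per leaver, neither taken from the protocol. It measures data discarded, not bias in any estimate. The correction should be made before analysis, but it does not threaten the design.

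**What to change.** Amend 11.4 and 11.8 to state the population by outcome:

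- **30-month TN, FN, sensitivity and specificity:** the visit 6/reference-standard requirement applies here and nowhere else. Section 11.4 should say so, so that it no longer claims all registered participants for this analysis.
- **Per-round positives, TP, FP and PPV:** all registered participants tested at that round, with unresolved LI-RADS 3/4 lesions counted as indeterminate, as in section 7.
- **Single-scan rounds:** one rule. Section 9.10 classes a visit with only one scan as missed, while 11.8 keeps it under intention to diagnose. The two must be reconciled, or the paired per-round denominators stay undefined.
- **Feasibility outcomes:** all registered participants except those who withdraw their data under option 3 of section 9.13.

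While 11.8 is open, its replacement clause should also be reconciled with section 9.13, which says: "Participants who withdraw will not be replaced as the sample calculation already allows for attrition".

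The cost is wording only; no additional data are needed. The drawback is that the per-round and 30-month tables will have different denominators, and each must be labelled with its own.

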11.5. Decision points

A decision point is planned at the end of July 2025 to assess the study feasibility. Stop / go criteria based on recruitment will be assessed at this point. By the end of July 2025, it is anticipated that 90 participants would be recruited and if this is achieved the study will continue. If fewer than 90 participants are recruited by end of July 2025 then the Steering Committee will decide on whether to continue the study considering the following numbers as a guide:

If at least 80 participants are recruited, consider continuing the study;

If fewer than 80 participants are recruited, consider stopping the study.

11.6. Stopping rules

The final decision to terminate the study at any point will rest with the Study Steering Committee.

11.7. The Level of Statistical Significance

Statistical significance will be set at p<0.05.

11.8. Procedure for Accounting for Missing, Unused, and Spurious Data.

Participants must attend the baseline and last visit (v6) and have at least one ceMRI (after a positive surveillance test, or as per protocol at the end of the study period) in order to be included in the final analysis. Participants who do not meet this will be removed and replaced for the purposes of the statistical analysis. All data from participants that fulfil this criterion will be used and analysed using intention to diagnose methods. This is to ensure that cases where a participant completes one surveillance test but not the other at a particular visit are still included. The diagnostic category of the missed test will be determined according to the diagnosis on that visit and the final diagnosis at the end of the study. In cases of HCC diagnosis, the missed test will be assigned as FN. In cases of FP results on the surveillance test performed at that visit, the missed test will also be assigned as FP.

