7. STUDY DESIGN

This will be a single-arm, multi-centre, prospective cohort study evaluating the diagnostic accuracy of nceMRI and USS for diagnosis of HCC in people at high risk of HCC. People at high risk of HCC include those with liver cirrhosis and a high risk of HCC, or those with previous successfully treated HCC who are back in surveillance with USS. Participants will be recruited from UK hospital-based liver clinics over a period of 18 months and study procedures will take place in UK hospitals and academic centres. Participants will undergo 6 rounds of 6 monthly surveillance with nceMRI and USS over 30 months. Participants will be invited to complete questionnaires at each study visit. Relevant data will also be extracted from the participants' medical records. If at any surveillance round, a surveillance test raises a concern for the presence of HCC, participants will undergo full diagnostic contrast enhanced MRI (ceMRI) to determine whether HCC is present or not. In cases where indeterminate lesions for HCC are reported, these may require further tests including contrast CT, follow-up contrast enhanced MRI, or biopsy as directed by the clinical team. All participants will undergo diagnostic full contrast enhanced MRI at the end of their study participation. If an HCC is diagnosed at any point in the study, then participants will receive treatment according to standard clinical protocols as part of standard of care.

Long-term follow up of medical records from NHS England, the NHS Central Register for Scotland and other patient registries may be conducted for up to 10 years after the end of the active follow up phase. Data obtained from these registries will include but is not limited to liver disease, decompensation episodes, HCC diagnosis, liver transplantation and death. There will be no additional involvement from study sites or participants, as the long-term follow up only involves accessing centrally held medical data.

The overall study design and participant flow is summarised in Figure 1.

Figure 1: AMULET study design and patient flow

Abbreviations: HCC: hepatocellular cancer; USS: ultrasound scan; nceMRI: non-contrast enhanced MRI; AFP: alpha-fetoprotein; HADS: hospital anxiety and depression scale; +ve: positive; -ve: negative [#] see section 9.4 for the description of the procedure for HCC risk estimation

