9.8.1. Description of comparator(s)

The comparator will be the diagnosis of hepatocellular carcinoma based on the typical features on contrast enhanced MRI or CT or histological diagnosis (biopsy or resection) or a consensus diagnosis of HCC as determined by the local MDT will be accepted as a diagnosis of HCC.

On study contrast enhanced MRI scans

For cases where a contrast enhanced MR is done following a positive surveillance test (on study ceMRI), lesions classified as LI-RADS 1 or 2 will be regarded as negative for HCC and lesions classified as LI-RADS 5 will be regarded as positive for HCC. Lesions classified as LI-RADS 3 or 4 will be regarded as indeterminate and will be followed up according to the local clinical routine. If LI-RADS 3 or 4 are designated as HCC by the local MDT, or they are proven to be HCC on biopsy, or they progress to LI-RADS 5 within the 30 months of follow-up then they will be defined as HCC for the analysis relating to the whole 30 month period of surveillance. In cases where LI-RADS 3 or 4 lesions remain under follow-up at the end of the 30 months follow-up without a clear classification as HCC or benign, or where they have been histologically proven to be benign, then they will be classified as negative for HCC for the purposes of the analysis. The classification of lesions at on-study ceMRI scans is shown below in Figure 2. The follow-up of LI-RADS 3 and 4 lesions in this situation will finish at the timepoint that visit 6 was due or at an earlier time point if a definitive classification is reached before then.

Figure 2: Flowchart for the classification of lesions detected on contrast enhanced MRI performed during the study following a positive surveillance test. In cases where lesions are determined as negative within the 30-month surveillance period, participants will re-enter the AMULET surveillance schedule until they complete the study. Where a positive for HCC diagnosis is made, participants will end their participation, will undergo no further surveillance and will be managed according to the recommendations of the local MDT. Participants with LI-RADS 3 or 4 lesions who are undergoing interval contrast enhanced imaging as recommended by the local MDT will be suspended from participation in AMULET.

End of Study contrast enhanced MRI scan

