9.11. Follow Up

Follow up visits/procedures after specific clinical outcomes (HCC diagnosis/liver transplant and death)

HCC Diagnosis

If a diagnosis of HCC is made during the study, no further in person follow up visits or nceMRI scans will take place. Follow up data will continue to be collected at 6 monthly intervals from hospital records.

Liver Transplant

If a participant receives a liver transplant during the study, no further in person follow up visits or nceMRI scans will take place. Follow up data will continue to be collected at 6 monthly intervals from hospital records.

Death

If a participant dies, the date and cause of death should be clearly documented using the 'Mortality' form within REDCap. In the event that a participant's death certificate is not available on hospital records, the local study team may be asked to contact the relevant GP to obtain date/cause of death data.

Long-Term Follow-up

The study teams will obtain data from NHS England, the NHS Central Register for Scotland and other patient registries on participants for up to 10 years after the last follow-up visit, phone call or email. This will be a passive follow-up with no participant involvement.

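### The final-analysis rule in section 11.8 requires attendance at visit 6, which no participant diagnosed with HCC before visit 6 can meet; it contradicts sections 9.8.1, 9.11, 9.13, 11.2 and 11.4

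*Protocol*

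**What the plan says.** Section 11.8 sets a joint condition for the final analysis: "Participants must attend the baseline and last visit (v6) and have at least one ceMRI". The bracket that follows allows the ceMRI to come either after a positive surveillance test or at the end of the study. It qualifies the ceMRI only, not the visit 6 requirement. The consequence of failing is explicit: "Participants who do not meet this will be removed and replaced for the purposes of the statistical analysis".

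Other sections make visit 6 unreachable for some participants:
- Section 9.11: "If a diagnosis of HCC is made during the study, no further in person follow up visits or nceMRI scans will take place".
- Section 9.8.1: "Where a positive for HCC diagnosis is made, participants will end their participation, will undergo no further surveillance".
- Section 9.8.1, on participants with LI-RADS 3 or 4 lesions having interval contrast imaging "as recommended by the local MDT will be suspended from participation in AMULET". The same section classes lesions still unresolved at the end of the 30 months as negative for HCC.

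Other sections point to a different analysis set:
- Section 11.4: "All participants registered will be included in the analysis".
- Section 11.2: "TP and FP will be determined at each visit as described above". It also counts interval cancers, and cancers found on an AFP-triggered ceMRI, as false negatives. Yet it takes the denominator of the 30-month table to be those who complete the study, and section 9.14 places a participant's end of study at month 30 (visit 6).
- Section 9.13 says that participants who withdraw are not replaced.

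**The concern.** The sensitivity comparison uses only participants with HCC. Taken literally, the section 11.8 rule removes from that comparison every cancer diagnosed before visit 6: true positives at the first five rounds, interval cancers, and AFP-triggered diagnoses counted as false negatives. The discordant pairs on which McNemar's test depends go with them.

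On the specificity side, the rule also drops participants whose LI-RADS 3 or 4 lesion is unresolved when visit 6 is due. Section 9.8.1 classes them as negative for HCC, and the notes to Figure 1 count the surveillance test that found the lesion as a false positive.

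This is not a detail that can wait for the SAP. The protocol fixes the rule. An SAP that follows it inherits the error, and one that departs from it contradicts the protocol. If the choice between the texts were made after data had been seen, the primary sensitivity result would be open to challenge.

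**Working it through.** **1. Can a participant with HCC diagnosed before visit 6 meet the rule?** Design (section 7): "Participants will undergo 6 rounds of 6 monthly surveillance with nceMRI and USS over 30 months". Five of the six rounds precede visit 6. After a diagnosis at any of them, or between them, sections 9.8.1 and 9.11 leave no further visit to attend. Nowhere does the protocol treat an HCC diagnosis as completing the study or waive visit 6. The answer is no, even with perfect compliance.

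**2. Reproduce the plan's figure.** Inputs from sections 11.2 and 11.3: McNemar's test, two-sided 5%, power 90%. The worked case is nceMRI sensitivity a = 0.80 and USS sensitivity b = 0.50, for which Table 2 gives 50 HCCs. The within-pair correlation φ is not stated.

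- c = φ·√[a(1−a)b(1−b)]; with φ = 0.1, c = 0.1 × √(0.8 × 0.2 × 0.5 × 0.5) = 0.02
- Discordant cells: 0.8 × 0.5 − 0.02 = 0.38 and 0.5 × 0.2 − 0.02 = 0.08, so p_d = 0.46; difference d = 0.30
- n = [1.960·√p_d + 1.282·√(p_d − d²)]² / d² = [1.960 × 0.678 + 1.282 × 0.608]² / 0.09 ≈ 49.4, rounded up to 50

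Independence (φ = 0) gives 55. With φ = 0.1 the formula matches all nine sensitivity cells of Table 2 and six of the seven numeric specificity cells. The exception, 98% against 95%, reads 2 where the formula gives 719; it may be a damaged table entry and has no bearing here. The value 0.1 is therefore an inference from Table 2.

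**3. How many HCCs survive the literal rule?** The protocol gives no distribution of diagnoses over rounds, so this is an assumption with a range:

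| Share of 50 HCCs first diagnosed at visit 6 | Kept | Lost |
|---|---|---|
| 10% | 5 | 45 |
| 1/6 (even spread) | about 8 | about 42 |
| 25% | about 13 | about 37 |
| 33% | about 17 | about 33 |

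**4. Power on what is left, 80% against 50%.** Power = Φ{[d√n − 1.960·√p_d] / √(p_d − d²)}. For n = 8: (0.849 − 1.329) / 0.608 = −0.79, so power is 0.21.

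| HCCs analysed | Asymptotic | Exact McNemar |
|---|---|---|
| 50 (planned) | 90% | 88% |
| 17 | 44% | 31% |
| 13 | 34% | 18% |
| 8 | 21% | 3% |
| 5 | 14% | 0% |

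The exact power at n = 5 is zero because five discordant pairs in one direction give a two-sided p of 2/32 = 0.0625.

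With 8 HCCs, 80% against 40% has 32% power (exact 8%). The widest assumed gap, 90% against 30%, has 60% (exact 33%).

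**The case against.** The best defence is that this is a drafting slip whose intent is clear from the surrounding text. Section 11.8 itself accepts a ceMRI prompted by a positive surveillance test and assigns a false negative to a missed test where HCC is diagnosed. Section 11.2 sets true positives visit by visit and counts interval cancers. Section 11.4 includes everyone registered. A sensible analyst would keep the early cancers. That stands as a reading of intent, and it means the power loss describes literal application rather than a likely result. It does not remove the contradiction, because the visit 6 condition has no exception and carries an explicit removal clause.

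Four stronger readings are tempting but not supported:
- **Nearly all detected cancers are lost.** The rule loses those diagnosed before visit 6, which is about five sixths under an even spread that the protocol does not state. Prevalent cancers at baseline would raise the loss. Counting LI-RADS 4 as HCC on the end-of-study ceMRI (section 9.8.1) would lower it.
- **The power figures show bias.** The cancers kept would include those seen only on the final ceMRI, which both tests missed, so the sensitivities themselves could shift. The calculation holds 80% and 50% fixed and shows only the effect of fewer cases.
- **All suspended LI-RADS 3 or 4 cases drop out and specificity is inflated by a known amount.** Lesions found negative within the 30 months return the participant to surveillance (section 9.8.1). Only those unresolved when visit 6 is due are affected, and their number is unknown.
- **Deaths and transplants without HCC are wrongly excluded.** They lack the end-of-study reference standard on which section 11.2 relies for true and false negatives, so leaving them out of the 30-month table is defensible.

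**Conclusion.** The concern holds as a contradiction in the rule that defines the primary analysis set, and it must be corrected before any analysis. As written, section 11.8 excludes every HCC diagnosed before visit 6 and every participant with a LI-RADS 3 or 4 lesion still suspended when visit 6 is due. It conflicts with sections 11.2 and 11.4 on who is analysed, and with section 9.13 on replacement, since a participant who withdraws before visit 6 also fails the rule.

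The size is conditional. It assumes literal application, 50 HCCs in total, 5 to 17 of them first diagnosed at visit 6, sensitivities of 80% and 50%, and a correlation of 0.1. The loss is serious across the whole of that range, so the conclusion does not depend on an even spread over rounds.

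**What to change.** Replace the inclusion rule in section 11.8 with one based on established HCC status. Suggested content: the 30-month analysis set is every registered participant who attended baseline and whose HCC status is established by the visit 6 due date, through either

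- (a) HCC confirmed by the reference standard on or before that date, with attendance at visit 6 not required; or
- (b) no HCC on the visit 6 ceMRI, or a LI-RADS 3 or 4 lesion classified under section 9.8.1 at that date.

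The date limit in (a) matters because registry follow-up runs for up to 10 years and could otherwise bring late cancers into the 30-month table. Require attendance at baseline, not both tests at baseline, so that the existing intention-to-diagnose handling of a single missed test is kept. Report participants with unknown status separately.

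Then align the related text: the completers denominator in section 11.2, the all-registered statement in section 11.4, and the replacement wording in sections 9.13 and 11.8, which should say one thing. The SAP should carry the same definition.

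The cost is a few sentences in a protocol amendment. It needs no new data, visits or scans.
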